14.5 AE/SAE reporting requirements and contact details

For any AE (including a SAE) all appropriate sections of the CRF must be completed.

Any SAE must be reported by the investigator to the Medical Monitor within 24 hours of awareness of the event via eCRF. Only in case of any problem with the eCRF the SAE must to be reported via fax:

This also applies to any significant AE, which in the investigator's opinion could affect the safety of the study subjects or the conduct of the study.

Information about an SAE will be collected and recorded on the SAE Report Form. The investigator will be requested to supply as much detailed information as possible regarding the SAE that is available at the time of the initial contact. The investigator should also complete missing or requested information and submit follow-up reports to the Medical Monitor until the SAE has resolved or, in the case of permanent impairment, until the SAE has stabilized.

The Medical Monitor will inform the sponsor about all SAEs without undue delay after receipt of the respective report from the Investigator.

Reporting to ECs and regulatory authorities will follow pertinent national legislation.

At the end of the study, a reconciliation of all reported SAEs will take place and be enclosed as a list in the Clinical investigation report (see Section 8.4).

14.6 AE/SAE follow-up

The investigator will take all appropriate and necessary measures required for resolution of the AE.

All AEs must be followed-up by the investigator until recovery, or until the investigator determines that the subject's condition is stable, or until the last day of the clinical investigation at the site, whichever occurs first.

Any pregnancy must be followed-up until the pregnancy outcome. If it is still on-going at the end of the clinical investigation, follow-up will be continued outside of the context of clinical investigation and pregnancy outcome (including pregnancy duration and health status of a newborn or cause of premature termination, as applicable) will be reported to the Sponsor.

All SAEs judged to be related to the investigational medical device (SADEs) must be followed by the investigator until the subject has recovered, recovered with sequelae, died, or until the investigator determines that the subject's condition is stable, whichever occurs first.

14.7 Foreseeable AEs and anticipated ADEs

Foreseeable AEs and anticipated ADEs are listed in Section 4.2 Anticipated adverse device effects.

14.8 Device deficiency reporting requirements

All investigational medical device deficiencies will be recorded on a Device Deficiency Report Form.

Device deficiencies should be reported by the investigator to the Medical Monitor within 24 hours after the site became aware of the device deficiency. Contact information is provided in Section 14.5.

The Medical Monitor will forward the deficiency report to the Sponsor within 24 hours after receipt of the respective report from the investigator.

If a device deficiency is associated with an AE, the corresponding AE documentation procedures must be adhered to as well.

14.8.1 Handling of deficient medical devices

Any medical device alleged to be deficient must not be used by the investigator and must be returned to the Sponsor.

14.9 Data monitoring committee

Not applicable.

15 Vulnerable populations

Vulnerable populations will not be included in this clinical investigation.

16 Suspension or premature termination of the clinical investigation

The Sponsor reserves the right to terminate the clinical investigation for any reason (e.g. safety, new data on the risk/benefit, ethical or administrative reasons). Written notice, outlining the reasons for the termination, will be submitted to the investigators in advance of such termination. The Sponsor will provide instructions if assessments beyond the regular per protocol procedures should be necessary.

The Sponsor may suspend enrolment or terminate the study at a specific site for reasons including, but not limited to, inadequate data collection, low subject enrolment rate, achievement of the total enrolment, or non-compliance with the CIP or other clinical research requirements.

The investigator, EC, or regulatory authority (if applicable) may also suspend or prematurely terminate the clinical investigation at the investigational sites for which they are responsible.

If the clinical investigation is prematurely terminated, the Sponsor or the Sponsor's representative will promptly inform the relevant authority (if applicable) of the termination and its reason(s); the investigator or the Sponsor (or representative) will promptly inform the EC, as specified in applicable regulations.

17 Publication policy

The results of the clinical investigation may be published and/or presented at scientific meetings. The results, however, should not be published without prior written consent by the Sponsor and such consent will not be unreasonably withheld. All manuscripts and abstracts, which refer to data originating from the clinical investigation, must be submitted to the Sponsor for comments at least 90 days prior to submission for publication.

If the proposed publication contains any invention related to the clinical investigation, the Sponsor is entitled to file respective patent applications and - on this ground - to delay the submission for publication or presentation of medical results for at least 6 months after receipt of the manuscript or abstract.

18 Bibliography

- ¹ Sjerobabski-Masnec I, Šitum M. Skin aging. Acta Clin Croat 2010; 49: 515-9.
- ² Newman J. Review of soft tissue augmentation in the face. Clin Cosmet Investig Dermatol. 2009; 2:141-50.

This statistical analysis plan (SAP) was defined by the sponsor and the responsible statistician. It is based upon the study protocol (version 3.0 of 31Oct2016) and contains detailed description of the statistical methods described therein.

The SAP describes prospectively the analyses to be performed on study data. It was finalized prior to enrolment of first study subject.

Study design and objectives

This is a prospective, open label, multicenter, post-market investigation to evaluate the performance and safety of Princess® VOLUME Lidocaine for the correction of nasolabial folds.

Following informed consent and screening, eligible subjects with moderate to severe nasolabial folds will be treated with Princess® VOLUME Lidocaine, and will return for follow-up assessments 2, 4, 24 and 36 weeks after the treatment. A touch-up treatment may be done at Week 2, if deemed appropriate by the investigator.

Princess® VOLUME Lidocaine is a sterile, biodegradable, viscoelastic, transparent, isotonic and homogenized injectable gel implant formulated in a physiologic buffer to a concentration of 23 mg/mL, with addition of 0.3% lidocaine hydrochloride. It is administered by injection into the deep dermis or subcutis. The volume applied depends on the size of the area which requires correction and will be selected by the investigator, but will not exceed 10 mL in total per treatment.

The performance of the investigational device will be evaluated by the investigator by assessing severity of nasolabial folds using the nasolabial folds severity rating scale (NLF-SRS) (4, 24 and 36 weeks after the treatment and in comparison to Day 0), global aesthetic improvement scale (GAIS) (4, 24 and 36 weeks after the treatment). The subject will evaluate pain intensity associated with the treatment (at Day 0 and at Week 2 (if touch-up treatment occurred)), and satisfaction with the treatment at 4, 24 and 36 weeks after the treatment.

The safety will be evaluated based on occurrence of adverse events, which will be collected throughout the investigation.

Number of subjects

Sample size calculation was performed by the sponsor. Up to 60 subjects with moderate to severe nasolabial folds will be enrolled in order to obtain the 24-week performance and safety data from at least 40 of them. If less than 60 subjects will be recruited at the point when at least 40 subjects complete the Week 24 assessment, a decision to continue the recruitment up to 60 subjects in total will be made by the sponsor. This sample size is arbitrarily selected and is considered appropriate for the post-market follow-up clinical investigation and sufficient to provide robust estimations on performance and safety parameters in the study population. With a sample size of 40 to 60, a two-sided 95% confidence interval for a single proportion using the large sample normal approximation will extend 0.076 to 0.093 from the observed proportion for an expected proportion of 0.900. Thus, a robust estimation of the success rate at week 24 can be derived.

Study and treatment duration

The duration of the clinical investigation will be 9 months for each participating subject. A single application of Princess® VOLUME Lidocaine, with optional Touch-up treatment after two weeks, if the desired level of correction has not been achieved with the initial application, is planned.

The total expected duration of the clinical investigation is about 13 months with an expected recruitment period of 3 to 4 months.

2 Performance and Safety Endpoints

2.1 Primary Performance Endpoints

The primary performance endpoints for this study are:

- The average change versus baseline (Day 0) in the NLF-SRS grade of nasolabial folds at Week 24 as evaluated by the investigator.
- The proportion of subjects with the NLF-SRS grade reduced by ≥1 point versus baseline at Week 24.

2.2 Secondary Performance Endpoints

The following secondary performance endpoints will be analyzed:

- The average change versus baseline in the NLF-SRS grade at Week 4 and Week 36 as evaluated by the investigator.
- The proportion of subjects with the NLF-SRS grade reduced by ≥1 point versus baseline at Week 4 and Week 36.
- The proportion of subjects with aesthetic improvement at Week 4, Week 24 and Week 36, as evaluated by the investigator using the global aesthetic improvement scale (GAIS)
- Subjects' satisfaction with aesthetic outcome of the treatment at Week 4, Week 24 and Week 36, as evaluated by the subject.
- The average pain intensity during and after the treatment, as evaluated by the subject using an 11-point numeric pain rating scale (NPRS) immediately after the last injection and 15 min. thereafter, respectively.
- The proportion of subjects with the NLF-SRS grade reduced by ≥1 point versus baseline at Weeks 24 as evaluated by the independent reviewer of photographs.

2.3 Safety Endpoints

Occurrence and frequency of adverse events (AEs).

2.4 Additional Endpoints

- The proportion of subjects with the NLF-SRS grade reduced by ≥2 points versus baseline at Week 4, 24 and Week 36.
- The proportion of subjects with the NLF-SRS grade reduced by ≥1 point versus baseline at Weeks 4 and 36 as evaluated by the independent reviewer of photographs.

3 Statistical Analysis Sets

3.1 Safety Analysis Set (SAF)

The safety analysis set (SAF) consists of all subjects who have been treated with the investigational device.

3.2 Intention-to-treat Population (ITT)

The intent-to-treat population (ITT) consists of all subjects who received the investigational device and had at least one post-treatment assessment (e.g., first pain assessment after injection).

3.3 Modified Intent-to-treat Population (modITT)

The modified intent-to-treat population (ITT) consists of all subjects who received the investigational device and had at least one post-treatment NLF-SRS assessment by the investigator.

3.4 Per-Protocol Set (PP)

All subjects who have received the investigational device and have completed the investigation without major clinical investigation plan deviations. Deviations from the protocol will be defined and classified during the data review meeting (see section 4.5). Subjects with major deviations from protocol will be excluded from the PP population.

3.5 Assignment of Analysis Sets to Analysis

The ITT will be considered the primary analysis set. All performance and additional endpoint analyses are based on the ITT. All primary endpoint analyses will be also performed for the modITT and PP. All secondary or additional endpoint analyses will be also performed for the PP. All safety analyses will be based on the SAF.

3.6 Visit Terminology

The following visit notation will be used for table, listing, and graph presentation:

Visit no.	Notation used on the case report form	Notation used for TLG		
1	VISIT 1 (Day 0)	Baseline		
2	VISIT 2 (Week 2 ± 2 days)	Week 2		
3	VISIT 3 (Week 4 ± 4 days)	Week 4		
4	VISIT 4 (Week 24 ± 7 days)	Week 24		
5	VISIT 5 (Week 36 ± 7 days)	Week 36		

4 Statistical Evaluation

Continuous variables will be presented using number of subjects with non-missing observations (N), mean, standard deviation (SD), median, minimum (min), maximum (max), 1st quartile and 3rd quartile. In general, min and max will be presented to the same level of precision as the raw data; means and medians, SD, and quartiles will be presented to one further decimal place. Categorical variables will be presented by frequency tables, using number and percentage. Percentages will be presented to one decimal place.

Baseline is defined as the measurements taken on Day 0 before treatment.

For each subject two facial folds (right and left) are rated per time point and grades (NLF-SRS and GAIS). As no great difference between those two folds is expected, the mean grade of both measurements will be calculated per time point.

4.1 Dispositions of Subjects and Analysis Sets

Disposition of subjects and analysis sets

The disposition of subjects and analysis sets, subjects per center, inclusion and exclusion criteria, and the status at study termination will be shown. In case subjects discontinue, the reason for discontinuation will be described.

The number of subjects available per visit will be presented.

4.2 Demographics and Other Covariates

Demographic data

Demographic data (age, gender, and race) will be tabulated. Age is derived from date of baseline – date of birth in days /365

Treatment application

Injection technique used, application of anesthetic cream (yes/no) will be tabulated using frequency tables by visit.

Basic statistics for number of devices used, injected total volume of right and left nasolabial fold will be given.

Pregnancy test

The results of the pregnancy test will be listed for females of childbearing potential only.

Previous and concomitant medication

Previous and concomitant medication will be coded according to World health organization drug dictionary (WHO-DD; June 2015).

Medications will be tabulated by anatomic group (ATC) level 4, and WHO-DD preferred term. The number of entries, as well as the number and percentage of affected subjects will be reported.

Previous and concomitant medications will be described separately.

- Previous medications are defined as all medication taken within 10 days (whether continuing or not) prior to Day 0.
- Concomitant medication is defined as all medication taken from Day 0 (including medications taken immediately pre-injection and post-injection) until Week 36.

If the start or stop date is incomplete and the allocation to previous or concomitant is not clear the medication will be considered to be concomitant.

Medical history will be listed only.

4.3 Performance Analysis

This is a non-comparative study and does not entail formal hypothesis testing. All primary and secondary variables will be analyzed using descriptive methods.

The individual NLF-SRS grades and the individual GAIS grades per visit will be calculated as the mean of grades assigned to the left and the right nasolabial fold, respectively.

The absolute NLF-SRS change from baseline will be computed by subtracting the value obtained at baseline from the value of the respective visit.

All adverse events (AE), AEs with relationship to the investigational medical device or procedure, and SAEs will be summarized by preferred term and system organ class.

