NLF-SRS grading of nasolabial folds⁰	X**		x	x	х
Urine pregnancy test ^d	X**				
Eligibility assessment	X**				
Treatment	Х	X§			
Photography	X**	X§	Х	х	Х
Pain assessment ^e	Х	xΩ			
GAIS assessment ^f			х	х	Х
Subject satisfaction ^g			Х	х	Х
Adverse events ^h	x***	Х	x	х	Х
Concomitant medication ^h	x***	х	х	х	х

* Includes screening and treatment.

** Prior to application of the investigational device

*** From beginning of the treatment onwards

- § Optional, to be done at investigator's discretion
- Ω To be performed only if Touch-up treatment occurred
- ^a Includes date of birth, sex, and race
- ^b All medication taken by the subject within the previous 10 days
- Performed by the investigator using the Nasolabial Folds Severity Rating Scale (NLF-SRS); the severity of the left and the right fold will be separately graded
- ^d In females of child-bearing potential only, including women who are postmenopausal for less than 12 months
- Evaluated by the subject immediately after injection and approximately 15 min. thereafter using an 11-point Numeric Pain Rating Scale
- ^f Evaluated by the investigator using the Global Aesthetic Improvement Scale (GAIS)
- ^g Evaluated by the subject
- ^h To be collected throughout the investigation, from beginning of the treatment until the last visit

List of abbreviations

ADE	Adverse device effect
AE	Adverse event
BDDE	1,4-butanediol diglycidyl ether
CIP	Clinical investigation plan
CRF	Case report form
DCF	Data clarification form
EC	Ethics Committee
eCRF	Electronic Case report form
GAIS	Global Aesthetic Improvement Scale
GCP	Good clinical practice
HA	Hyaluronic acid
IB	Investigator's brochure
ICF	Informed consent form
MedDRA	Medical Dictionary for Regulatory Activities
mIU	Milli-international unit
NLF	Nasolabial fold
NLF-SRS	Nasolabial Folds Severity Rating Scale
NPRS	Numeric Pain Rating Scale
PT	Preferred term
SADE	Serious adverse device effect
SAE	Serious adverse event
SAP	Statistical analysis plan
SOC	System organ class
TMF	Trial master file
USADE	Unanticipated serious adverse device effect
UV	Ultraviolet
w/w	Weight/weight

Table of contents

Арр	Approval and signature pages		
Syno	opsis	5	
Sche	edule of procedures and events	8	
List	of abbreviations	9	
1	Background	. 13	
2	Identification and description of the investigational device	. 13	
2.1	Device description	. 13	
2.2	Manufacturer	. 14	
2.3	Intended use and mode of administration	. 14	
2.4	Traceability	. 14	

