6.4.5 NLF-SRS grading of nasolabial folds

NLF-SRS is a validated, 5-point rating scale ranging from Grade 0 (none) to Grade 4 (extreme) as outlined in

Table **3**3 and 4. The severity of nasolabial folds will be evaluated by the investigator according to the NLF-SRS. The left and right nasolabial fold will be separately graded, and the assigned grades will be recorded in the subject's record and the CRF.

 Table 3. Nasolabial Folds Severity Rating Scale (NLF-SRS)

 Table 4 CROMA - NLF Severity Rating Scale (NLF-SRS)

CROMA NLF-	Description
------------	-------------

SRS grade	
0	None/minimal: No visible/minimal nasolabial folds
1	Mild: Shallow but visible nasolabial fold with a slight indentation
2	Moderate: Moderately deep nasolabial fold
3	Severe: Very deep nasolabial fold with prominent facial feature
4	Extreme: Extremely deep and long nasolabial fold with skin redundancy

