7.4.1 Performance endpoints

As two facial folds of each subject will be considered, there are two measurements per subject for NLF-SRS. No great differences between the folds are expected, thus the mean of both measurements will be used for analyses. Individual NLF-SRS grades per visit will be calculated as the mean of grades assigned to the left and the right nasolabial fold, respectively. The absolute NLF-SRS change versus baseline will be computed by subtracting the value obtained on Day 0 from that of the corresponding visit. Absolute NLF-SRS change from baseline will be summarized by the visit using descriptive statistics and additionally the 95% confidence intervals of the mean will be given. In addition, the proportion of the NLF-SRS change values ≥ 1 , or ≥ 2 , respectively, will be calculated.

Individual GAIS grades, subjects' satisfaction with aesthetic outcome, and pain ratings will be summarized and tabulated by visit using descriptive statistics.

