4.3.2 Analysis of Secondary Performance Endpoints

All secondary performance endpoints will be analyzed for the ITT and PP

Basic statistics for the average grade of NLF-SRS will be tabulated by visit. The change from baseline in the average grade of NLF-SRS as assessed by the investigator to Week 4 and 36 will be summarized with descriptive statistics for continuous variables.

The proportion of subjects with the average grade of NLF-SRS as assessed by the investigator reduced by ≥1 point versus baseline will be summarized with frequency tables at Week 4 and 36.

The proportion of subjects with aesthetic improvement at Week 4, 24, and 36, as assessed by the investigator will be tabulated using frequency tables. Aesthetic improvement is defined as having a GAIS grade < 4 (yes/no).

GAIS categories:

- 1 very much improved
- 2 much improved
- 3 improved
- 4 no change
- 5 worse

The proportion of subjects with the average grade of NLF-SRS as assessed by the independent reviewer of photographs reduced by ≥1 point versus baseline will be summarized with frequency tables at Week 24.

Subjects' satisfaction with aesthetic outcome of the treatment will be summarized with frequency tables at Week 4, 24 and 36 and displayed via individual profile plots.

Pain will be assessed twice after treatment by means of an 11-point numeric pain rating scale (NPRS).

Improvement in pain score will be categorized as follows:

- Yes: Pain score second assessment pain score first assessment < 0
- No: Pain score second assessment pain score first assessment > 0
- Equal: Pain score second assessment pain score first assessment = 0

Resulting pain scores and improvement in pain score (yes/no/egual) will be tabulated with frequency tables by assessment (first and second) and visit in case of touch-up treatment. Further, basic statistics will be provided for the pain scores and the change between first and second pain score (= score at second assessment - score at first assessment).

4.4 **Analysis of Additional Endpoints**

All additional endpoints will be analyzed for the ITT and PP.

The proportion of subjects with the average grade of NLF-SRS as assessed by the investigator reduced by ≥2 points versus baseline will be summarized with frequency tables at Week 4, 24 and 36.

The proportion of subjects with the average grade of NLF-SRS as assessed by the independent reviewer of photographs reduced by ≥1 point versus baseline will be summarized with frequency tables at Week 4 and 36.

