4.8 Miscellaneous

For qualitative variables the frequencies (absolute and relative) are calculated. If no further remark is given in the description of the tables following format will be used for all tables with qualitative variables:

	Y-variable(s)							
	Category 1		Category 2		Total			
X-variable(s)	N	%	N	%	N	%		
category 1								
category 2	4							
missing								
Total		100.0		100.0		100.0		

For this standard format the description of the tables in Appendix A determines only the X- and Y-variables. If another format of table is described in the details to the tables, the real design will be determined by the technical possibilities within SAS and may not look identical to the provided example. However, all information as displayed will be included.

Quantitative parameters will be described by declaring the mean value, standard deviation, minimum, first quartile, median, third quartile, and maximum. In the description of the tables this will be denoted by "basic statistics".

The listings are always sorted by center and subject. If a different sorting order should be used for some listings this will be remarked separately. The variables for the special listings are explicitly given in the description of listings. All listings will be presented for the safety analysis set, if not stated differently, and indicator variables for further analysis sets, e.g., ITT, will be added.

The following title will be used for all generated tables and listings:

CROMA – VINO Page # of #

The numbering NNN of the tables/listings/graphs will be stated in the detailed description (Appendix A).

Following footnote will be used for all generated tables, listings, and graphs:

, <Actual date> Author: <Author of program> Program: <Name of program>

The statistical evaluation will be performed using SAS version 9.3 or higher.

<Subtitle for description of contents - if applicable>

<Analysis set>

6 Deviations from the Protocol

- · Additional endpoint are included and will be analyzed:
 - o The proportion of subjects with the NLF-SRS grade reduced by ≥2 points versus baseline at Week 4, 24 and Week 36.
 - o The proportion of subjects with the NLF-SRS grade reduced by ≥1 point versus baseline at Weeks 4 and 36 as evaluated by the independent reviewer of photographs.
- An additional study population will be considered, the modified ITT for the primary endpoint.

7 Signatures

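### Does averaging GAIS over the two folds in the SAP, when the protocol averages only NLF-SRS, leave the aesthetic improvement endpoint undefined?

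*SAP*

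**What the plan says.** **SAP.** The opening of section 4 (Statistical Evaluation) says: "For each subject two facial folds (right and left) are rated per time point and grades (NLF-SRS and GAIS"). It then takes the mean of the two, on the ground that the folds should differ little. Section 4.3 repeats the derivation: "The individual NLF-SRS grades and the individual GAIS grades per visit will be calculated as the mean of grades assigned to the left" and right folds. Section 4.3.2 sets the cutoff: "Aesthetic improvement is defined as having a GAIS grade < 4 (yes/no"), on a scale from 1 (very much improved) to 5 (worse), where 4 is no change.

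**Protocol.** Fold-level grading appears twice, both times for NLF-SRS. Section 6.4.5 says "The left and right nasolabial fold will be separately graded", and the NLF-SRS footnote to Table 1 says "the severity of the left and the right fold will be separately graded". The GAIS footnote to that table and section 6.4.6 mention neither left nor right. Section 7.4.1 averages NLF-SRS: "Individual NLF-SRS grades per visit will be calculated as the mean of grades assigned to the left and the right nasolabial fold, respectively". For GAIS it says only: "Individual GAIS grades, subjects' satisfaction with aesthetic outcome, and pain ratings will be summarized and tabulated by visit using descriptive statistics".

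**Declared deviations.** SAP section 6 lists two additional endpoints and one further item: "An additional study population will be considered, the modified ITT for the primary endpoint". GAIS is not mentioned.

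**The concern.** The SAP appears to give a named secondary endpoint a data structure that the protocol does not describe, without declaring it. Two of the five GAIS category descriptions in the protocol's Table 5 refer to the patient, which suggests one grade per subject. If so, the SAP's averaging step has no pair of grades to work on.

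If GAIS is instead graded by fold, the mean can take values such as 2.5 or 3.5, which are not GAIS categories. A subject with one improved fold and one unchanged or worse fold can then be counted as improved. At stake is the proportion of subjects with aesthetic improvement at Weeks 4, 24 and 36. The primary endpoints, the safety analysis and the sample size do not use GAIS.

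**Working it through.** **Inputs.** GAIS grades 1 to 5 and the cutoff below 4 (SAP 4.3.2); the left/right mean (SAP 4 and 4.3); n = 40 to 60 and an expected proportion of 0.900 (SAP, Number of subjects).

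**The plan's own precision figure.** Half-width = 1.96 × √(0.9 × 0.1 / n).
- n = 40: 0.0930
- n = 60: 0.0759

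These reproduce the stated 0.093 and 0.076.

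**Reading 1: one GAIS grade per subject.** The cutoff applies directly to the grade g, and g < 4 means g is 1, 2 or 3. The averaging sentences are redundant and the proportion is the same with or without them. SAP 4.3.2 fits this reading: it writes of an average grade for NLF-SRS each time, but simply of a grade for GAIS.

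**Reading 2: one GAIS grade per fold.** There are 15 unordered pairs.
- Both folds at 1 to 3: 6 pairs. The largest mean is (3 + 3)/2 = 3.0, so all count as improved.
- Both folds at 4 or 5: 3 pairs. The smallest mean is (4 + 4)/2 = 4.0, so none counts.
- One fold at 1 to 3 and the other at 4 or 5: 3 × 2 = 6 pairs.

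| Discordant pair | Mean | Mean < 4 | Both folds < 4 | Either fold < 4 |
|---|---|---|---|---|
| (1,4) | 2.5 | yes | no | yes |
| (2,4) | 3.0 | yes | no | yes |
| (3,4) | 3.5 | yes | no | yes |
| (1,5) | 3.0 | yes | no | yes |
| (2,5) | 3.5 | yes | no | yes |
| (3,5) | 4.0 | no | no | yes |

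The SAP rule counts 5 of the 6, a both-folds rule none, and an either-fold rule all 6. Concordant pairs are classified identically by all three. The table shows possible patterns, not frequencies.

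**Size under Reading 2, against a both-folds rule.** One subject in the first five rows adds 1/40 = 2.5 points or 1/60 = 1.7 points. The documents give no discordance rate. Entry requires roughly symmetrical folds (protocol 6.3.4), so I assume 0 to 3 such subjects:
- n = 40: 0 to 3/40 = 7.5 points
- n = 60: 0 to 3/60 = 5.0 points

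Exceeding the half-widths above would take 4/40 = 10.0 points or 5/60 = 8.3 points. That comparison is only for scale: the half-widths refer to the Week 24 success rate, and SAP 4.3.2 plans no interval for GAIS.

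**Same convention on the primary scale.** If one fold improves by 2 NLF-SRS grades and the other by 0, the mean reduction is (2 + 0)/2 = 1.0. The subject is then a responder at the 1-point threshold. The protocol accepts this for a primary endpoint, for the same reason that the SAP gives for both scales.

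**The case for a change.** The best case for a change is that SAP section 6 declares even an extra descriptive responder threshold, so a new derivation for a secondary endpoint belongs there too. The mean rule is also awkward: a subject with one worse fold counts as improved if the other fold is graded 1 or 2, but not if it is 3, although 3 is itself an improved category. That is neither a both-folds nor an either-fold rule, and no reason specific to GAIS is given. Two or three sentences would settle it.

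Part of this stands. The difference exists, it is not listed, and SAP 4.3.2 leaves the reader to infer from sections 4 and 4.3 that the cutoff falls on a mean.

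The rest does not require a change. The protocol is silent on fold-level GAIS and does not forbid it, and its section 7 leaves analysis detail to the SAP, so an added derivation is not clearly a departure that section 6 must list. The three SAP statements together classify every pair, so no choice is left open. Half-grades do no harm in a yes/no classification, which is the only GAIS result SAP 4.3.2 specifies. Whether a mean, both folds or either fold should define improvement is a matter on which reasonable statisticians differ.

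**Conclusion.** The wording of the two documents differs, but the endpoint is defined and can be computed under either way of recording GAIS. With one grade per subject, the effect on the reported proportion is zero. With a grade per fold, the SAP rule is explicit in substance and follows the protocol's NLF-SRS convention. The gap from a stricter both-folds rule is 2.5 points per affected subject at n = 40 and 1.7 at n = 60, or at most 7.5 and 5.0 points if no more than 3 subjects are affected.

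That limit of 3 is an assumption, supported only by the symmetry required at entry. The case report form and the SAP's table specifications are not in the text available, so I cannot say which reading applies. The analyst will see that from the data, and the SAP rule works in both cases. What remains is a matter of documentation for a descriptive secondary endpoint with no hypothesis test. No change to the plan is needed.
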